15.7.2.2. Handling of Missing data for Statistical Analysis

Element	Reporting Detail
Snapshot	
 In the Snapshot dataset, participants without HIV-1 RNA data in the assessment window for the visit of interest (due to missing data or discontinuation of IP prior to the visit window) do not belong to 'HIV-1 RNA < 50 c/mL (or <200 c/mL)'. The nature of this missing data will be further classified in Snapshot summaries as either 'HIV-1 RNA ≥ 50 c/mL' (or "HIV-1 RNA ≥ 200 c/mL') or 'No Virologic Data at Week X'; Appendix 9: Snapshot Algorithm Details for full details
LOCF	
 In the LOCF dataset, missing values will be carried forward from the previous, non-missing available on-treatment assessment. If the baseline value is missing any missing values until the first non-missing value will remain missing.
Lipid LOCF	
Baseline for Lipids LOCF Analyses:
 
 Last evaluable lipids assessment up to and including the start of IP, where 'evaluable' is defined as: Lipid modifying agents not taken within 12 weeks of the date of assessment and Lipids are collected in a fasting state. Participants with unevaluable Baseline for Lipids (as defined above) will be excluded from this dataset. 
During the Maintenance:
 
 If participants initiate serum lipid-lowering agents during the maintenance, then the last available fasted on-treatment lipid values prior to the initiation will be used in place of future, observed on-treatment values. Imputation at visits with observed on-treatment values will continue even if the participant discontinues the lipid-lowering agent. Missing assessments will not be imputed 
Analyses Evaluated with Lipid LOCF Dataset:
 
This dataset will be used to summarize fasting lipids parameters in the following displays: Summary of Fasting TC/HDL ratio Change from Baseline Summary of Fasting Lipids Percentage Changes from Baseline
 
All other displays of lipids (e.g. toxicity tables and NCEP tables) will use observed fasting data, without LOCF imputation.

15.8. Appendix 8: Values of Potential Clinical Importance

ECG values of potential clinical importance are defined as $QTc > 500$ msec or increase from baseline in $QTc \geq 60$ msec.

15.9. Appendix 9: Snapshot Algorithm Details

Detailed Algorithm Steps		

 • Consider an analysis visit window for Week X as defined in Table 10. • The HIV-1 RNA threshold of 50, 200 c/mL will be analysed, respectively, in this study • The analysis window ‘Week 48’ and HIV-1 RNA threshold of ‘50 c/mL’ are used for the purpose of illustration. A participant’s Snapshot response and reason at Week 48 are categorized as below. 
 ○ HIV-1 RNA < 50 c/mL ○ HIV-1 RNA ≥ 50 c/mL 
 Data in window not below 50 Discontinued for lack of efficacy Discontinued for other reason while not below 50 Change in background therapy* ○ No Virologic Data at Week 48 Window 
 Discontinued study due to AE or death Discontinued study for other reasons On study but missing data in window 
* Note: since permanent change in ART are not permitted in this protocol, all such participants who permanently change ART will be considered ‘HIV-1 RNA ≥ 50 c/mL’ if the permanent change in ART is made prior to an analysis timepoint. Participants with protocol permitted oral bridging treatment or a temporary change in ART prior to an analysis timepoint (e.g. participant took the ART different from study treatment during oral lead-in by mistake for a short period and then went back to the study treatment) will not be considered ‘HIV-1 RNA ≥ 50 c/mL’ due to ‘change in ART’.
 
 • The steps in determining response and reasons are indicated in the table below, in the order stated: 		
Detailed steps		
Please note that the following scenarios will NOT be penalized Per Snapshot algorithm (i.e. please exclude these scenarios from Condition 1-4).		

 • Dose reduction, dropping a component, or change in formulation (e.g. ‘Tivicay + Kivexa’ to ‘Triumeq’ with the identical ingredients) 		
Condition (‘Week 48’ indicates Week 48 window)	Response	Reasons
1. If non-permitted change in background therapy prior to Week 48	HIV-1 RNA ≥ 50	Change in background therapy
2. If permitted change ^[a] in background therapy prior to Week 48 AND the latest on-treatment VL prior to/on the date of change is ≥ 50 c/mL (NA to this study)	HIV-1 RNA ≥ 50	Change in background therapy

3. If non-permitted change in background therapy during Week 48		

 Last on-treatment VL during Week 48 prior to/on the date of change ≥ 50 c/mL 	HIV-1 RNA ≥ 50	Data in window not below 50

 Last on-treatment VL during Week 48 prior to/on the date of change < 50 c/mL 	HIV-1 RNA < 50	

 No VL during Week 48 prior to/on the date of change 	HIV-1 RNA ≥ 50	Change in background therapy
4. If permitted change ^[a] in background therapy during Week 48 AND the last on-treatment VL prior to/on the date of change is ≥ 50 c/mL (NA to this study)		
4.1 this last on-treatment VL occurs prior to Week 48	HIV-1 RNA ≥ 50	Change in background therapy
4.2 this last on-treatment VL occurs during Week 48 but prior to/on the date of change	HIV-1 RNA ≥ 50	Data in window not below 50
5. If none of the above conditions met		
5.1 On-treatment VL available during Week 48		

 Last on-treatment VL during Week 48 ≥ 50 c/mL 	HIV-1 RNA ≥ 50	Data in window not below 50

 Last on-treatment VL during Week 48 < 50 c/mL 	HIV-1 RNA < 50	
5.2 No on-treatment VL during Week 48		
5.2.1 If participants still on study, i.e. a participant has not permanently discontinued the study treatment yet, or if a participant permanently discontinued the study treatment and the upper bound of analysis snapshot window is prior to the following date: Q8W arm: Min[max(Date of last injection + 63, Date of Last Dose of Oral CAB+RPV + 1), Withdrawal Date] Q4W arm: Min[max(Date of last injection + 35, Date of Last Dose of	No virologic data at Week 48 Window	On study but missing data in window

Oral CAB+RPV + 1), Withdrawal Date] , where 'Withdrawal Date' refers to the date the participant failed to complete per corresponding conclusion form.
		

5.2.2 If participants withdraw before/during Week 48 due to
		

5.2.2.1 Safety reasons (e.g. AE/death, liver chemistry stopping criteria, renal toxicity withdrawal criteria, QTc withdrawal criteria etc, as recorded in eCRF Conclusion form)
	
No virologic data at Week 48 Window
	
Disc due to AE/death

5.2.2.2 Non-safety related reasons (e.g. Lack of efficacy, protocol deviation, withdrew consent, loss to follow-up, study closed/terminated, investigator discretion etc, as recorded in eCRF Conclusion Form)
		

 • Last on-treatment VL <50 c/mL OR no on-treatment VL available during study 	
No virologic Data at Week 48 Window
	
Disc for other reasons

 • Last on-treatment VL ≥ 50 c/mL AND withdrawal due to Lack of efficacy 	
HIV-1 RNA ≥ 50
	
Disc. for lack of efficacy

 • Last on-treatment VL ≥ 50 c/mL AND withdrawal due to all other non-safety related reasons 	
HIV-1 RNA ≥ 50
	
Disc. for other reason while not below 50

a. Excluding permitted change in background therapy where change or decision to change is made prior to/on the first on-treatment viral result

Examples from FDA guidance

Data in Window

Virologic outcome should be determined by the last available measurement while the patient is on treatment and continued on trial within the time window:

- HIV-1 RNA = 580 c/mL at Day 336, HIV-1 RNA below 50 c/mL on Day 350. This should be categorized as HIV-1 RNA below 50 c/mL.

No Data in Window

Discontinued study due to Adverse Event or Death:

- Any patient who discontinues because of an AE or death before the window should be classified as *Discontinued due to AE or Death* (as appropriate), regardless of the HIV-1 RNA result, even if the HIV-1 RNA is below 50 c/mL at the time of discontinuation.
- However, if a patient has an HIV-1 RNA value in the time window and also discontinues in the time window, the viral load data should be used to classify the patient's response. This is the Virology First hierarchy:

- a. HIV-1 RNA below 50 c/mL at Day 336 and discontinues because of AE or even dies on Day 360 — this person is categorized as having HIV-1 RNA below 50 c/mL.
- b. HIV-1 RNA is 552 c/mL on Day 336 and the patient discontinues on Day 360, the patient is categorized as having HIV-1 RNA \geq 50 c/mL.

Discontinued for Other Reasons:

- Only patients who have achieved virologic suppression can be counted as *Discontinued for Other Reasons*.
- If a patient discontinues the study before the time window because of *lack of efficacy* then the patient should be included in the HIV-1 RNA \geq 50 row and not in the Discontinued for Other Reasons row.
- If a patient discontinues because *participant withdrew consent* and his or her HIV-1 RNA result at the time of discontinuation was equal to or above 50 c/mL, then he or she should be categorized as HIV-1 RNA \geq 50 and NOT as Discontinued for Other Reasons.
- If a patient discontinued because of *Lost to Follow-Up* and the last HIV-1 RNA result was 49 c/mL, then the patient can be categorized as Discontinued for Other Reasons.
- If patients changed background treatment — *not permitted by protocol*— they should be considered an efficacy failure and captured in the HIV-1 RNA \geq 50 c/mL row.

On study but missing data in window:

- If there are no data during Days 294 to 377, but there is an HIV-1 RNA below 50 c/mL on Day 380, this patient should be considered *On Study but Missing Data in Window*.
- If there are no data during Days 294 to 377, but there is an HIV-1 RNA equal to or above 50 c/mL on Day 280, this patient also should be classified as *On Study but Missing Data in Window*.

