Design Features	
 Study 207966 (Antiretroviral Therapy as Long Acting Suppression every 2 Months-ATLAS-2M) is a Phase IIIb, randomized, open-label, active-controlled, multicenter, parallel-group, non-inferiority study designed to assess the antiviral activity and safety of CAB LA + RPV LA administered every 4 weeks compared CAB LA + RPV LA administered every 8 weeks in approximately 1020 adult HIV-1 infected patients. The ATLAS-2M study comprises a Screening Phase (up to 35 days), and a Maintenance Phase (Day 1 to Week 100), followed by an Extension Phase (post Week 96). Additionally, any participant who receives at least a single dose of CAB LA and/or RPV LA and discontinues the CAB LA + RPV LA regimen will enter the Long-term Follow-up Phase and will initiate highly active antiretroviral therapy (HAART) for 52 weeks after the last dose of CAB LA and/or RPV LA, or until the assigned CAB LA + RPV LA regimen is locally approved and commercially available. Two groups of patients who fulfill eligibility requirements will be randomized (1:1) at Day 1 to receive CAB LA + RPV LA Q4W, or CAB LA + RPV LA Q8W regimen for at least 100 weeks: 
 Group 1: Patients randomized from current ART Standard of Care (SOC) therapy Group 2: Patients currently receiving CAB LA + RPV LA Q4W
Dosing	
 Group 1: oral therapy with CAB 30 mg + RPV 25 mg once daily at Day 1 for 28 days (± 3 days) to determine individual safety and tolerability, followed by CAB LA + RPV LA Q4W or CAB LA + RPV LA Q8W (as randomized at Day 1) Group 2: CAB LA + RPV LA Q4W or CAB LA + RPV LA Q8W (as randomized at Day 1)
Time & Events	
 Refer to Appendix 2: Schedule of Activities

Overview of Study Design and Key Features	
Treatment Assignment	
 • Randomized (1:1) at Day 1 to receive CAB LA + RPV LA Q4W or CAB LA + RPV LA Q8W • GSK RandAll NG used to generate randomization schedules • Stratified Randomization by prior CAB+RPV exposure (0 weeks, 1 to 24 weeks, >24 weeks)

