7.1.4. Strategy for Intercurrent (Post-Randomization) Events

As defined by the Snapshot algorithm, HIV-1 RNA ≥ 50 c/mL is determined by the last available HIV-1 RNA measurement while the participant is on treatment within the analysis visit window of interest.

Participants without on-treatment HIV-1 RNA data for the visit of interest and who discontinue treatment for reasons not related to adverse event while having HIV-1 RNA ≥ 50 c/mL at time of discontinuation or who change study treatment not permitted per protocol before the analysis window are classified as having HIV-1 RNA ≥ 50 c/mL.

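### Appendix 9 exempts a dropped component from the Snapshot change-of-therapy conditions, while the note beside it scores every permanent ART change as HIV-1 RNA ≥50 c/mL, so a permanent stop of CAB or RPV alone has two classifications

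*SAP*

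**What the plan says.** Four places in the SAP bear on this point.

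- **Appendix 9, starred note.** It states that "since permanent change in ART are not permitted in this protocol, all such participants who permanently change ART will be considered" HIV-1 RNA ≥50 c/mL if the change precedes the analysis timepoint. Two exceptions follow: "Participants with protocol permitted oral bridging treatment or a temporary change in ART prior to an analysis timepoint" are not scored as failures on this ground.
- **Appendix 9, head of the detailed steps.** The instruction reads "Please note that the following scenarios will NOT be penalized Per Snapshot algorithm (i.e. please exclude these scenarios from Condition 1-4"), and the bullet under it lists "Dose reduction, dropping a component, or change in formulation". The one example is a switch between branded oral products with the same ingredients. Neither product is part of the study regimen.
- **Appendix 9, Conditions 2 and 4 (permitted changes).** These are marked as not applicable; Condition 2, for instance, ends "prior to/on the date of change is ≥ 50 c/mL (NA to this study"). The exemption bullet carries no such mark.
- **Section 7.1.4.** Participants "who change study treatment not permitted per protocol before the analysis window are classified as having HIV-1 RNA" ≥50 c/mL. Section 7.1.5.1 repeats the rule and refers to Section 15.9 for full details.

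Section 2.3 adds that anyone who has received CAB LA and/or RPV LA and "discontinues the CAB LA + RPV LA regimen will enter the Long-term Follow-up Phase" and start other therapy.

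**The concern.** The exemption has no time limit and is not confined to changes that leave the ingredients the same. In a multi-drug oral regimen, dropping a component may leave an active combination. Here it leaves a single drug. The note and the exemption therefore reach opposite results for a permanent stop of one study drug, and both govern the algorithm behind the primary endpoint (≥50 c/mL at Week 48) and the key secondary endpoint (<50 c/mL at Week 48).

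At stake is whether suppression measured on one of the two drugs is credited to the arm's two-drug regimen. The trial is open-label, so settling the question once such a participant has appeared would mean choosing the rule with the outcome and the arm in view.

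**Working it through.** **Classification.** Take a participant who permanently stops one of CAB or RPV before the Week 48 window (Study Days 295 to 378, Table 10), continues the other, and has a last in-window viral load <50.

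| Step | Under the exemption bullet | Under the starred note |
|---|---|---|
| Conditions 1 to 4 | Skipped | Condition 1 applies (non-permitted change before Week 48) |
| Condition 5.1 | Applies if the viral load is on-treatment | Not reached |
| Result | HIV-1 RNA <50 | HIV-1 RNA ≥50 |

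*Is that viral load on-treatment?* Table 16 counts time from the last injection (plus 63 days for Q8W, 35 for Q4W) or the last oral CAB+RPV dose. Its footnote applies these limits only to participants who have permanently discontinued study treatment; all assessments for everyone else are on-treatment. Neither rule requires both drugs, so Table 16 does not resolve the conflict.

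*What if the drug is stopped inside the window?* Condition 3 would use the last viral load up to the date of change. The exemption would also admit later values. The two routes can differ here too.

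*Do other sections settle it?* Appendix 1, criterion 03, keeps permanent changes in ART regimen as ≥50 in the per-protocol Snapshot analysis, in line with the note. Section 7.1.4 opens its sentence with participants who lack on-treatment data, so it could be read more narrowly. Section 7.1.5.1 states the rule without that opening.

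**Scale.** The SAP gives no figure on this point to reproduce, and no expected failure rate. Inputs from the SAP are 510 per arm, a 4% margin (Section 1) and the Sato variance (Section 7.1.5.1). Assumptions are one stratum and equal starting failures y in both arms.

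With n = m = 510: N = 1020 and W = nm/N = 255.

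- Change in the arm's proportion per participant: 1/510 = 0.196, about 0.20 points.
- d = x/n − y/m; P = (n²y − m²x)/N² (the last term is zero when n = m); Q = [x(m − y)/N + y(n − x)/N]/2; variance = (dP + Q)/W²; upper limit = d + 1.96 × √variance.

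Worked case, y = 10:

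- x = 10: d = 0, P = 0, Q = 4.902. Variance = 4.902/65,025 = 0.00007539, SE = 0.008682, upper limit = 1.70%.
- x = 11: d = 0.001961, P = −0.25, Q = 5.142. Variance = (−0.00049 + 5.142)/65,025 = 0.00007907, SE = 0.008892, upper limit = 1.94%.

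The shift is 0.24 points. Repeating for other starting counts:

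| Failures per arm | Upper limit, equal arms | One extra Q8W failure | Shift (points) |
|---|---|---|---|
| 2 | 0.77% | 1.05% | 0.29 |
| 5 | 1.21% | 1.46% | 0.25 |
| 10 | 1.70% | 1.94% | 0.24 |
| 20 | 2.38% | 2.61% | 0.22 |
| 25 | 2.65% | 2.87% | 0.22 |

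One extra Q4W failure lowers the upper limit instead, by 0.11 points at 2 failures per arm and 0.17 at 25. From 10 failures per arm, non-inferiority is lost only at 10 extra Q8W failures (upper limit 4.03%). The corresponding counts are 12 extra from 5 per arm and 8 extra from 20 per arm.

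**The case against.** **A rule with an exception is not a contradiction.** The instruction comes after the note and says plainly what to skip, and Section 7.1.5.1 defers to Appendix 9. On this reading a change in ART means a switch to other drugs, and a programmer gets one answer. That reading is possible, but the SAP does not state it. The note lists its own exceptions and a dropped component is not among them. Telling programmers to remove these scenarios from Conditions 1 to 4 implies that they could otherwise fall there. The example from another regimen and the background-therapy wording suggest text carried over rather than a choice made for this trial.

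**The design does not plan for single-drug treatment.** Section 2.3 sends anyone leaving the regimen to long-term follow-up and other therapy, and for those not continuing into Extension, Table 14 ends the Maintenance Phase at that start. This stands as a reason to expect few cases. It does not classify a participant who departs from that path.

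**The per-protocol analysis would catch it.** Under-dosing for at least 10% of time on treatment is an exclusion criterion in Appendix 1. Exclusion is decided case by case and leaves the primary ITT-E classification unchanged.

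**The endpoint stays virologic.** This stands: an exempted participant whose last in-window value is ≥50 is still a failure.

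**Two stronger readings are tempting.** A reader might infer that exempting dose reduction lets a move between the randomised regimens go unscored. The SAP does not show that a dose reduction is a change in ART. Its examples in Appendix 1 have 3 mL for Q8W injections and 2 mL for later Q4W injections, so neither move is plainly a reduction. A reader might also infer that the exemption favours non-inferiority. The wording applies to both arms alike: credit in Q8W lowers the upper limit, and credit in Q4W raises it.

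**Conclusion.** The conflict is in the text and bears on the primary and key secondary endpoints. It concerns a permanent stop of one study drug. Temporary changes and permitted oral bridging are already covered by the note, and dose reduction needs clarifying but is not shown to be in conflict with it.

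The likely effect is small. Each reclassified Q8W participant moves the upper limit by about 0.22 to 0.29 points against a 4% margin, assuming 510 per arm, one stratum and 2 to 25 failures per arm. The number of such participants cannot be derived from the SAP and should be low. The case for acting rests on having one rule fixed in advance for a stated primary-endpoint definition. It does not rest on an expected change in the trial's conclusion.

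**What to change.** Before database freeze, reconcile the exemption in Appendix 9 with the starred note and Section 7.1.4. Either of two edits would do it:

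- limit the Snapshot exemption to a change of formulation with identical ingredients, together with the temporary changes and permitted oral bridging that the note already excepts; or
- mark the dropped-component item as not applicable to this study, as was done for Conditions 2 and 4.

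Then align the on-treatment definition in Table 16 with the chosen rule, so that viral loads after a permanent stop of one study drug are handled consistently. Also say how dose reduction in Appendix 9 relates to the under-dosing deviations in Appendix 1. If the exemption was meant to cover a permanent stop of one drug, the note and Section 7.1.4 should say so instead. Which treatment changes are permitted is a matter for the protocol.

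The cost is a few sentences in the SAP and one programming condition, with no new data and no change to sample size.

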15.10. Appendix 10: Variables Defined for Time to Event Analysis

Programming Instructions for the Kaplan-Meier analysis of treatment-related discontinuation equals failure (TRDF)		
Condition	Censor Status	Event Description/AVAL
1. Participant met CVF event criteria during the Maintenance Phase (based on derived CVF)	CNSR=0	EVNTDESC=CVF AVAL=Study Day of SVF* *immediately preceding CVF
2. Participant with Maintenance Phase withdrawal due to ' Lack of Efficacy ', ' Treatment Related AE ', ' Intolerability due to Injection ', or ' Protocol Defined Safety Stopping Criteria ' during Maintenance Phase Note: primary reason and/or standardized subreason for discontinuation based on Maintenance Conclusion form in the eCRF. ' Protocol Defined Safety Stopping Criteria ' includes GSK defined liver chemistry stopping criteria, renal toxicity criteria and QTc withdrawal criteria. Treatment Related AE' is defined as participants who have primary reason for withdrawal =AE and who have at least one AE considered drug related and leading to withdrawal/permanent discontinuation of investigational product.	CNSR=0	EVNTDESC= terms in italic, respectively. For Q4W arm: AVAL= min [Study Day of Maintenance Phase Discontinuation, max(Study Day of Last Injection + 35, Study Day of Last Dose of Oral CAB+RPV + 1)] For Q8W arm: AVAL= min [Study Day of Maintenance Phase Discontinuation, max(Study Day of Last Injection + 63, Study Day of Last Dose of Oral CAB/RPV + 1)] Note: Date of Maintenance Phase discontinuation is from the Maintenance Phase Conclusion form in the eCRF.
If none of the above conditions met		
3. Participant with Maintenance Phase withdrawal due to other reasons	CNSR=1	EVNTDESC='Censored due to Study Discontinuation for Other Reasons' AVAL will be defined as the same as above 2
4. Participant who did not have premature withdrawal from	CNSR=1	EVNTDESC='Censored due to data cutoff for analysis'

Programming Instructions for the Kaplan-Meier analysis of treatment-related discontinuation equals failure (TRDF)		
Condition	Censor Status	Event Description/AVAL
the Maintenance Phase		
AVAL = Study Day of last on-treatment date during the maintenance phase, which is defined as follows:
 
For Q4W arm: min [Study Day of Nominal Week 100 Visit, Study Day of LTFU ART Start Date, Study Day of Last Contact Date at time of analysis, max(Study Day of Last Injection + 35, Study Day of Last Dose of Oral CAB+RPV + 1)]
 
For Q8W arm min [Study Day of Nominal Week 100 Visit, Study Day of LTFU ART Start Date, Study Day of Last Contact Date at time of analysis, max(Study Day of Last Q8W IM Dose + 63, Study Day of Last Dose of Oral CAB+RPV + 1)]

Note that last injection and last dose of oral CAB+RPV mentioned in table above are only applied to participants who permanently discontinued from the study treatment. The similar approach will be used to derive for Kaplan-Meier analysis of efficacy-related discontinuation equals failure (ERDF), except that the reason of withdrawal in Condition 2 will be restricted to 'Lack of Efficacy'.

